3.4 Randomization

During the Screening/Baseline period, all subjects will be assigned a screening identifier, which will include the center number and subject number. If the subject fulfils all eligibility criteria during the Screening/Baseline period, a study eye will be assigned (prior to randomization) and the subject will be randomized in a 2:1:2 ratio to receive either timrepigene emparvovec high dose $(1.0 \times 10^{11} \text{ vg})$, timrepigene emparvovec low dose $(1.0 \times 10^{10} \text{ vg})$ or to enter the untreated Control group.

Randomization will be generated using a validated system that automates the random assignment of treatment groups and stratified by surgical group*. Once a subject is deemed

Biogen /	NightstaRx,	Ltc
BIIB111		

eligible, the investigative site (or authorized designee) will access the system, and the subject will be randomized using a standard blocked randomization.

Once a subject has been randomized, a change in "study eye" designation is not permitted.

At the time of randomization, a projected surgical date should be defined for each subject. For each subject randomized to the control group, this projected surgical date (+/-1 day) should remain the Day 0 (Visit 2) date. For each subject randomized to a treated group, Day 0 will be the actual date of surgery.

All subjects' data (including screen failures) will be entered into the electronic case report form (eCRF).

* A surgical group will consist of a single 'Surgical Site' and 'Non-surgical Sites'. The Surgical Site will conduct baseline and follow-up visits for local subjects, as well as surgeries and immediate post-operative visits for all subjects treated in the surgical group. The 'Non-surgical Sites' will only perform the baseline/screening visit and the follow-up visits from Day 7 (Visit 4) onwards for their respective local subjects.

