analysis, with extra scientific rigor, multiple imputation will also be applied to Month 12 BCVA collected more than 2 months prior or 3 months after the visit window not due to COVID-19. Assuming the BCVA at different visits follows a multivariate normal distribution, the Monte Carlo Markov Chain (MCMC) will be implemented to impute all missing data and the Month 12 BCVA collected more than 2 months prior or 3 months after the visit window (Schafer 1997, Schafer 1999). Each imputed data for continuous endpoint, analysis of covariance (ANCOVA) model including surgical group, baseline value of the assessment, and study arms will be applied. For binary endpoint, the proportion difference and the corresponding standard error between the treatment groups (i.e. high dose vs. placebo, low dose vs. placebo) will be calculated for each imputed dataset using the two-sample Binomial test. Analysis will be performed for each of the 100 imputed datasets and results will be combined by Rubin's rule (Rubin 1976, Rubin 1987) for inference assuming the statistics estimated from each imputed dataset are normally distributed. The Sample SAS code is in Appendix 4.

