10.2 Key Secondary Endpoints

The three key secondary endpoints and the corresponding primary analysis are as summarized and presented by pre-specified order in Table 1.

Biogen /	NightstaRx, Ltd
BIIB111	

The continuous efficacy endpoint will be analyzed by the analysis of covariance (ANCOVA) model including surgical group, baseline value of the assessment, and study arms. Missing data will be handled by the last observation carried forward (LOCF) approach.

The binary efficacy endpoints will be analyzed with the same method used for the primary efficacy endpoint with missing values imputed as failure.

The least square (LS) means, standard error (SE) and 95% CI will be reported for each treatment at each post-randomization visit. Least square mean, SE, 95% CI, and p-value for the between group differences will also be provided.

The primary analysis of the key secondary endpoints will be based on the ITT population, and supportive analyses will be performed based on the PP population and the randomized population. When performing the supportive analysis based on the randomized population, for subjects who do not have any post-baseline assessments, the baseline will be used when LOCF approach is applied (i.e. the change from baseline will be zero). Knowing the patients who had BCVA below 34 ETDRS letters at Month 12 for study eye, if any, will at site not be the responders of subjects with a ≥ 10 -letter improvement from Baseline in BCVA at Month 12, these subjects with minor protocol deviation will be included in the supportive analysis of the secondary endpoint of Proportion of subjects with a ≥ 10 -letter improvement from Baseline in BCVA at Month 12 measured by the ETDRS chart based on the PP population. When performing the supportive analysis based on PP population for the secondary endpoints of (a) Change from Baseline in BCVA at Month 12 measured by the ETDRS chart and (b) Proportion of subjects with no decrease from Baseline in BCVA or a decrease from Baseline in BCVA of <5 ETDRS letters at Month 12 measured by the ETDRS chart, subjects at site who had BCVA below 34 at Month 12 will be excluded from these analyses. The background information for site is described in Section 8.

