Additional supportive analysis will be conducted by comparing the study eyes vs. the fellow eyes (i.e., contralateral control) within the low dose and the high dose treatment groups. The binary efficacy endpoints will be analyzed at the Month 12 visit using the paired McNemar test. Change from baseline in BCVA at Month 12 will be compared between the study eye and the fellow eye using the linear mixed model where the two eyes are considered correlated within each patient. The model will contain the variables for baseline BCVA, treatment groups (low dose and high dose), surgical group, eye (study eye vs fellow eye) and the treatment*eye interaction, where the eye variable acts as the repeat variable. (See sample SAS code in Appendix 5).

	Key Secondary Endpoint	Statistical Method
1	Change from Baseline in BCVA at Month 12 measured by the ETDRS chart	ANCOVA
2	Proportion of subjects with a ≥10-letter improvement from Baseline in BCVA at Month 12 measured by the ETDRS chart	Fisher's Exact Test; Fisher's Exact-Boschloo test with a Berger-Boos correction of beta=0.001; CMH Approach
3	Proportion of subjects with no decrease from Baseline in BCVA or a decrease from Baseline in BCVA of <5 ETDRS letters at Month 12 measured by the ETDRS chart	Fisher's Exact Test; Fisher's Exact-Boschloo test with a Berger-Boos correction of beta=0.001; CMH Approach

Tabla 1	Statistical Tests	for Vor	Secondamy	Efficient	Endnointe
Table 1	Statistical Lesis	IUI KEY	Secondary	Efficacy	Enapoints

Biogen / NightstaRy	x, Ltd
BIIB111	

Abbreviations: BCVA= best corrected visual acuity, CHM= choroideremia, ETDRS=Early Treatment of Diabetic Retinopathy Study

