 - The same process will be used for all other visits. Subjects whose missing data were imputed at previous visits will contribute to the imputation for the next visit.
 - The regression imputation model includes an intercept and the slopes of the measurements from all previous visits.
- 3. Analyze each imputed complete dataset.
- 4. Combine estimates from the results of each model.

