14.6 Appendix 6: Mixed Model Repeated Measures – Sample SAS Code

14.7 Appendix 7: Multiple Imputation based on MNAR – Sample SAS Code

```
*** make the data monotone missing ***;
PROC MI DATA=dset OUT=dset1 NIMPUTE=100 SEED=1234;
BY TRT:
VAR BASELINE VISIT2 VISIT3 VISIT4 VISIT5 VISIT6;
MCMC chain=multiple impute=monotone;
RUN;
*** for control arm, use all available data to impute missing data ***;
PROC MI DATA=dset1(where=(TRT='Placebo')) out=dset2 nimpute=1 seed=1235;
BY IMPUTATION ;
VAR BASELINE VISIT2 VISIT3 VISIT4 VISIT5 VISIT6;
MONOTONE REG(VISIT2=BASELINE/details);
MONOTONE REG(VISIT3=BASELINE VISIT2/details);
MONOTONE REG(VISIT4=BASELINE VISIT2 VISIT3/details);
MONOTONE REG(VISIT5=BASELINE VISIT2 VISIT3 VISIT4/details);
MONOTONE REG(VISIT6=BASELINE VISIT2 VISIT3 VISIT4 VISIT5/details);
RUN;
*** for active arm, impute missing data on VISIT2 using control arm ***;
PROC MI DATA=dset1(where=((TRT='Active' and VISIT2=.) or (TRT='Placebo'
                                                                                 and
VISIT2>.))) out=dset3 nimpute=1 seed=1235;
BY IMPUTATION ;
VAR BASELINE VISIT2;
MONOTONE REG(VISIT2=BASELINE/details);
RUN;
*** for active arm, impute missing data on VISIT3 using control arm ***;
PROC MI DATA=dset3(where=((TRT='Active' and VISIT3=.) or (TRT='Placebo'
                                                                                 and
VISIT3>.))) out=dset4 nimpute=1 seed=1235;
BY IMPUTATION ;
VAR BASELINE VISIT2 VISIT3;
MONOTONE REG(VISIT3=BASELINE VISIT2/details);
RUN:
*** repeat the same method for each sequential visit in active arm ***;
*** set all data together ***;
*** DSETX is the subset of active subjects with missing on VISIT2 ***;
*** DSETY is the subset of active subjects without missing on VISIT2 ***;
Data dsetall;
Set dset2 dsetX dsetY;
RUN:
*** Analyze the data on the last timepoint by ANCOVA ***;
PROC MIXED data=dsetall;
BY IMPUTATION ;
CLASS TRT;
MODEL CHG=BASELINE TRT;
LSMEANS TRT / PDIFF CL;
ESTIMATE "High vs Control" TRT 1 0 -1;
ESTIMATE "Low vs Control" TRT 0 1 -1;
ODS OUTPUT LSMEANS=LSMEAN;
ODS OUTPUT ESTIMATES=LSEST;
RUN:
*** Use Rubin's Rule ***;
PROC MIANALYZE parms=lsest;
BY LABEL;
MODELEFFECTS ALLEST;
ODS OUTPUT PARAMETERESTIMATES=PARMS;
RUN:
```

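### Sample code in SAP Appendices 4, 5 and 7 omits surgical group, the randomisation stratum: it contradicts the SAP text for the first two, and for the missing-not-at-random analysis the text names no covariates to correct it

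*SAP*

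**What the plan says.** SAP Section 3.4 describes a system that "automates the random assignment of treatment groups and stratified by surgical group". The SAP text then carries that stratum into its models for BCVA change:

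- **Main analysis, first key secondary endpoint (SAP 10.2):** "analysis of covariance (ANCOVA) model including surgical group, baseline value of the assessment, and study arms".
- **Missing-at-random (MAR) multiple imputation (SAP 5.5):** the "model including surgical group, baseline value of the assessment, and study arms will be applied" to each imputed dataset. The section refers to Appendix 4 for code.
- **Study eye versus fellow eye (SAP 10.2):** "The model will contain the variables for baseline BCVA, treatment groups (low dose and high dose), surgical group, eye", plus the treatment-by-eye interaction. It refers to Appendix 5 for code.
- **MMRM sensitivity analysis (SAP 10.4.2):** surgical group is listed among the terms.

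The protocol synopsis (Statistical Methodology) sets the same three-term ANCOVA, with Surgery Group, for continuous endpoints in general.

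For the MNAR control-based imputation, SAP 10.4.3 describes the imputation in detail. For the analysis, step 3 says only "Analyze each imputed complete dataset". The section refers to Appendix 7, where the analysis step is labelled as an ANCOVA and the statement is "MODEL CHG=BASELINE TRT". Appendix 4 (14.4.1) has the same statement. Appendix 5 models eye, treatment, their interaction and baseline. None of the three blocks has surgical group in its CLASS or MODEL statement.

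**The concern.** A missing-data sensitivity analysis is easiest to read when it changes the missing-data assumption and nothing else. SAP 10.4.3 relies on that kind of reading: agreement of the MNAR result with the main result is to be taken as showing robustness. If the main ANCOVA adjusts for the stratum and the sensitivity ANCOVA does not, two things change at once.

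A programmer working from Appendices 4 and 5 also has two specifications that disagree, and the SAP does not say whether text or code prevails. For MNAR, the section itself names no covariates, so the programmer must either follow the code or infer the model from elsewhere. Adjusting for a stratification factor also recovers whatever outcome variance that factor explains. Leaving it out gives up that gain in the between-arm comparisons.

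**Working it through.** **1. Text against code**

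| Analysis | Terms in the text | Terms in the sample code |
|---|---|---|
| Main ANCOVA (SAP 10.2) | surgical group, baseline, arm | none given |
| MAR imputation (SAP 5.5; Appendix 4) | surgical group, baseline, arm | baseline, arm |
| Study versus fellow eye (SAP 10.2; Appendix 5) | baseline, arm, surgical group, eye, arm × eye | baseline, arm, eye, arm × eye |
| MNAR imputation (SAP 10.4.3; Appendix 7) | no covariates named | baseline, arm |
| MMRM (SAP 10.4.2; Appendix 6) | includes surgical group | no code visible in the public copy; not checked |

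The MAR and eye rows are contradictions. The MNAR row is a gap in the text, filled by code that differs from the main model. The MNAR *imputation* model is stated in the text, also without surgical group, and its code agrees. The discrepancy there is confined to the analysis model.

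**2. The plan's own figures are not touched**

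The stated power (SAP 3.6) is for an unstratified two-sided Fisher test and reproduces with a 16.7% response rate:

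- 56 per arm, no control responders: significance needs 6 high-dose responders (6 v 0, p = 0.027; 5 v 0, p = 0.057). Power is 92.3%, against at least 90% stated.
- 64 per arm, exactly one control responder: significance needs 8 (8 v 1, p = 0.033; 7 v 1, p = 0.062). Power is 85.9%, against 85% stated.

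**3. Precision of the between-arm ANCOVAs (Appendices 4 and 7)**

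Let R² be the share of residual variance that surgical group explains. The documents give no value, so a range is assumed. With arms balanced within groups, the standard error without the stratum, relative to that with it, is about 1/√(1 − R²):

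- R² = 0.05: 1/√0.95 = 1.026, or 2.6% larger
- R² = 0.10: 1/√0.90 = 1.054, or 5.4% larger
- R² = 0.15: 1/√0.85 = 1.085, or 8.5% larger

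The formula ignores the degrees of freedom spent on the groups and the between-imputation variance in Rubin's rules, so these figures are approximate.

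**4. Type I error**

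A simulation on complete data (1,500 runs per setting; assumed 8 surgical groups of 20, allocation 2:1:2 blocked within group) gave, for high dose versus control at the 0.05 level:

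| R² | Stratum omitted | Stratum included | SE ratio |
|---|---|---|---|
| 0 | 0.044 | 0.046 | 1.000 |
| 0.05 | 0.041 | 0.043 | 1.027 |
| 0.10 | 0.046 | 0.059 | 1.055 |
| 0.20 | 0.029 | 0.045 | 1.120 |

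Monte Carlo error is about √(0.05 × 0.95/1500) = 0.006. Omission is neutral to conservative. The SE ratios agree with the formula.

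**5. Shift in the estimate**

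With the same layout and exact balance within groups, dropping the stratum moved the high-dose versus control estimate by about 0.005 residual SD. The standard error is about √(1/64 + 1/64) = 0.18 residual SD. Imperfect balance in practice would make the shift larger.

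**6. The eye contrast (Appendix 5)**

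Both eyes of a subject belong to the same surgical group, and the text model has no group-by-eye term, so the group effect nearly cancels from the within-subject contrast. Generalised least squares with the same layout and an assumed within-pair correlation of 0.4 showed a change in that standard error of under 0.02% at R² of 5%, 10% and 15%.

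**The case against.** The appendices are headed as sample code, and Appendix 7 is plainly a template. It has two arms called Active and Placebo in a three-arm trial with no placebo, a comment in place of the later visits, and placeholder dataset names. An omitted covariate in such code is weak evidence of intent. For the MAR and eye analyses the text gives the model in full. For MNAR, the protocol's general ANCOVA for continuous endpoints and the Section 10.2 ANCOVA for this endpoint supply a default that a careful statistician would adopt.

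Much of this stands, and it rules out several stronger readings that a reader might draw:

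- *Appendix 7 is the only model available for the MNAR analysis.* It is not, because the protocol synopsis and SAP 10.2 offer a default. What remains is that Section 10.4.3 does not refer to that default and points instead to code that departs from it.
- *A difference between the MNAR and main results could not be attributed to missing data.* That goes too far. Randomisation is blocked within surgical group, so the estimate should move little, and the main effect is a somewhat wider interval.
- *All three code blocks lose precision.* The within-subject contrast in Appendix 5 does not, to any useful extent.
- *The false-positive rate is inflated.* The simulation shows no sign of this.

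The sample-code label does not remove the need for a correction. Nothing in the SAP says the text overrides the code, and for MNAR the section has no covariate list that could do so.

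**Conclusion.** The point holds as a minor inconsistency in supportive and sensitivity analyses. Appendices 4 and 5 contradict the models stated in SAP 5.5 and 10.2. The Appendix 7 analysis model differs from the Section 10.2 ANCOVA that the MNAR analysis is meant to test, and Section 10.4.3 does not settle which applies.

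If the code were run as printed, the MAR and MNAR between-arm comparisons of BCVA change would have standard errors about 2.6% to 8.5% larger. That rests on the assumption that surgical group explains 5% to 15% of residual variance; the true share could lie outside that range. For the eye comparison the defect is the mismatch alone. The primary Fisher test, the main key secondary ANCOVA, the testing hierarchy and the stated power are unaffected.

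**What to change.** 1. In SAP 10.4.3 step 3, state that each imputed dataset is analysed with the Section 10.2 ANCOVA: surgical group, baseline value and study arm.
2. Add surgical group to the CLASS and MODEL statements in Appendices 4, 5 and 7. In Appendix 5, keep the existing order of treatment and eye in CLASS, because the ESTIMATE coefficients depend on it.

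The cost is one sentence and one term in three code blocks. The variable is already collected, and the main ANCOVA already makes the same adjustment. It uses one degree of freedom per group beyond the first. With the 8 groups assumed above and 160 subjects, residual degrees of freedom would go from 160 − 4 = 156 to 149.

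This aligns the analysis models only. The imputation models would still carry group differences only through baseline and earlier visits. Whether to add surgical group there is a separate choice, on which the MNAR text and code already agree.
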